7.0 SUBJECT ENROLLMENT

Clinical site personnel will review the patient's medical history for eligibility. Potential candidates will be fully informed of the purpose of the study and the nature of the implantation procedure. The implantation procedure will be described and its potential risks and benefits will be explained in detail. Once the patient's potential eligibility has been determined, the Investigator will discuss the study and ask the patient if they are interested in participating in the study. Patients who voluntarily agree to participate in the trial will be asked to sign and date the written Informed Consent Document (ICD). The study will be explained to the patient in lay terms. The ICD, approved by the site Institutional Review Board (IRB), must be signed by the potential study participant before he or she undergoes any study specific assessments. A copy of the signed and dated ICD should be provided to the subject. Failure to obtain a signed ICD prior to the procedure constitutes a protocol deviation. Subjects must be informed that they may withdraw from the study at any time, and for any reason, and will continue to receive therapy as indicated by their physician.

All subjects who meet the eligibility criteria and give written informed consent are considered enrolled in the study and must be entered into the electronic database for assignment of subject identification number. This unique number identifies each Case Report Form (CRF) and should be used on all source documents so that study data is reported in anonymous form to protect subject confidentiality.

A screen-failed subject refers to a subject who signed the approved ICD but failed to meet all the eligibility criteria. There are no follow-up requirements for subjects who electively withdraw from the study prior to treatment. The original ICD and a screening log will be maintained in the clinical site's study files. No CRFs are required to be completed for screen failure patients and these patients will not be followed per the Investigational Plan requirements.

If the Investigator is unable to place a MobiusHD implant in a subject, the subject will be followed to the 30-Day visit and will then be exited from the study in the absence of any ongoing adverse events. If an adverse event is ongoing or not stabilized, the subject will continue to be followed until complete resolution or stabilization of the AE with no expectation or need for further treatment. The reason(s) for failure to place the implant will be documented on the Procedure CRF.

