1.0 PROTOCOL SYNOPSIS

TITLE	CALM-FIM_US - C ontrolling and L owering Blood Pressure with the M obiusHD™ - A Prospective Multicenter Safety Study
STUDY OBJECTIVE	To evaluate the safety and performance of the MobiusHD system in subjects with resistant hypertension.
STUDY DESIGN	
This is an open-label, multicenter, first-in-man clinical trial to be conducted inside the United States. Eligible subjects with stage 2 resistant systemic arterial hypertension currently being treated with a minimum of three (3) anti-hypertensive drugs, who consent to study participation will be assigned to treatment with the MobiusHD system.
 
Potential study participants will be consented and then screened at two (2) baseline visits beginning at least 30 days prior to MobiusHD placement. Qualified patients will undergo placement of the MobiusHD under angiographic visualization, and will then be followed for 36 months.
 
Subjects will be enrolled in two (2) phases, as follows:
 
 ▪ Ten subjects will be implanted unilaterally and followed for seven (7) days. ▪ Based on consensus following 7-day clinical outcome analysis by an independent data safety monitoring board (DSMB), 10 additional subjects will be enrolled and implanted bilaterally.
PATIENT POPULATION	Subjects with resistant hypertension receiving at least three (3) anti-hypertensive medications including a diuretic and with no evidence of extracranial carotid disease or significant great vessel/aortic arch atherosclerotic disease.
NUMBER OF PATIENTS	Twenty subjects are to be enrolled at two (2) to ten (10) U.S. clinical sites.
PRIMARY OUTCOME	Safety: Incidence of serious adverse events (SAEs) and unanticipated adverse device effects (UADE) reported for the study population from implantation through six (6) months of follow-up.
SECONDARY OUTCOME	Performance: Decrease in office cuff blood pressure (BP).
ADDITIONAL OUTCOMES	
Change in heart rate
 
Reduction of medication post 6-month follow-up
 
365-Day safety and efficacy
 
Long term safety and efficacy – one (1) to three (3) years

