6.1 INCLUSION CRITERIA

Candidates for this study must meet the following criteria to be enrolled in the study, as determined in the following screening and baseline visits:

Baseline Screening Visit 1 – (Day 0 – 14) – Assessed on Day 14

1. Provided written informed consent;
2. ≥ 18 years of age and ≤ 80 years of age;
3. Office cuff SBP ≥ 160 mmHg measured per protocol instructions (Appendix VI) following at least one (1) month of maximally tolerated therapy with at least three (3) anti-hypertensive medications, of which at least one (1) must be a diuretic. Any combination medications will be counted per the active ingredient (for example, Zestoretic (Lisinopril +HCTZ) equals two (2) anti-hypertensive medications);
4. Renal artery imaging performed within the last 12 months showing no evidence of renal artery stenosis. Acceptable imaging modalities include renal duplex, magnetic resonance angiography, CT angiography, and selective or nonselective renal angiography depending on investigator site diagnostic standards. In the absence of adequate imaging testing this inclusion criteria could also be met by obtaining a renal duplex prior to enrollment or by performing nonselective renal angiography at the time of device implantation.
5. Compliant with medications (self-reported) and daily blood pressure readings – Subject must be a minimum 80% compliant with diary entries; and
6. For females (with child-bearing potential), a negative pregnancy test and the use of a medically accepted method of birth control for the duration of the trial.

Baseline Screening Visit 2 – (Day 15 – 30) - Assessed on Day 30

1. No significant obstructive vascular disease on CTA or MRA of the aortic arch and great vessels;
2. Carotid duplex studies demonstrating no obstructive carotid disease;
3. Continued adherence to hypertension medications without anticipated changes and daily blood pressure readings – Subject must be a minimum 80% compliant with diary entries;
4. Continued office cuff SBP ≥ 160 mmHg despite at least one (1) month of therapy at maximally tolerated therapy with at least three (3) anti-hypertensive medications, of which at least one (1) must be a diuretic. Any combination medications will be counted per the active ingredient (for example, Zestoretic (Lisinopril +HCTZ) equals two (2) anti-hypertensive medications).

Day of Procedure -

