6.2 EXCLUSION CRITERIA

Candidates will be ineligible for enrollment in the study if any of the following conditions are identified at the screening or baseline visits:

Baseline Screening Visit 1 – (Day 0 – 14) – Assessed on Day 14

1. Known or clinically suspected baroreflex failure or autonomic neuropathy;
2. Hypertension secondary to an identifiable and treatable cause other than sleep apnea (e.g., hyperaldosteronism, renal artery stenosis, pheochromocytoma, Cushing's disease, coarctation of the aorta, hyperparathyroidism and intracranial tumor);
3. Treatable cause of resistant hypertension including, but not limited to, improper BP measurement, volume overload and pseudotolerance (excessive sodium intake, volume retention from kidney disease, inadequate diuretic therapy), drug-induced or other causes (non-adherence, inadequate doses, inappropriate combinations, NSAIDs, COX-2 inhibitors, cocaine, amphetamines, or other drugs, sympathomimetics, oral contraceptives (confirmed cause of resistant hypertension), adrenal steroids, cyclosporine, and tacrolimus, erythropoietin, licorice (including some chewing tobacco), ephedra, ma haung, bitter orange); and excessive alcohol intake;
4. Arm circumference greater than 46 cm and/or BMI \geq 40;
5. Chronic atrial fibrillation;
6. Vulnerable plaque or ulceration of any size in the carotid artery or aortic arch;
7. History of bleeding complications with dual anti-platelet therapy in the past or has known uncorrectable bleeding diathesis;
8. Current use of additional anticoagulation therapy. Examples include vitamin K antagonists like warfarin, direct thrombin inhibitors, direct factor Xa inhibitors, thrombin IIa inhibitors like apixaban, rivaroxaban, dabigatran and etexilate;
9. Peptic ulcer disease with documented active ulcer or bleeding within the last year;
10. History of allergy to contrast dye that cannot be managed medically;
11. History of orthostatic hypotension;
12. History of syncope within the last six (6) months;
13. History of myocardial infarction or unstable angina within the past three (3) months;
14. History of cerebral vascular accident (stroke or TIA) within the past year;
15. Severe chronic kidney disease (calculated GFR < 45 ml/min);
16. Prior surgery, radiation, or endovascular stent placement in either carotid region;

17. Clinically significant structural valvular cardiac disease;

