18. Moderate to severe reactive airway disease, chronic obstructive pulmonary disease, or primary pulmonary hypertension;
19. Uncompensated congestive heart failure or known severe reduction in left ventricular function (EF < 30%);
20. Uncontrolled co-morbid medical condition that would adversely affect participation in the trial;
21. Non-controlled diabetes mellitus;
22. Active infection within the last month;
23. Co-morbid condition that reduces life expectancy to less than one (1) year;
24. Mental health issues that would prohibit the subject's ability to meet the protocol requirements;
25. Currently taking an imidazoline receptor agonist or receiving central sympathetic treatment;
26. Enrolled in a concurrent clinical trial;
27. Unable or unwilling to fulfill the protocol follow-up requirements;
28. Subject is a prisoner or member of other protected population;
29. Planned surgery or other procedure within the next six (6) months; or
30. Deep venous thrombosis (DVT) within the last year or documented recurrent DVT.

Baseline Screening Visit 2 – (Day 15 – 30) - Assessed on Day 30

1. ICA lumen diameters < 5 mm or > 11.75 mm within the planned location of the device placement via CTA or MRA;
2. Carotid hypersensitivity detected by carotid massage or typical history, as described in the study protocol; and
3. Significant aortoiliac or common femoral artery disease that will prohibit safe femoral access.

Day of Procedure – Angiographic

1. Evidence of plaque, ulceration or any stenosis by angiographic evaluation in orthogonal views of the carotid artery. Lumen diameters will be assessed to exclude subjects with ICA lumen diameters smaller than 5 mm or larger than 11.75 mm within the planned location of the device placement;
2. Any plaque or ulceration on the arch angiogram involving the aortic arch and/or the origin of the great vessels;
3. Inappropriate anatomy of the carotid bifurcation for deployment of the MobiusHD, including, but not limited to, tortuosity of the extracranial vessels and significant angulation of the common carotid artery bifurcation; and

4. Type III arch or horizontal takeoff of the left carotid from the innominate and calcification of the carotid bulb.

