8.4 SELECTION AND SCREENING OF SUBJECTS

Prior to subject participation in this study, the study team must obtain written IRB/EC approval for the Protocol and the ICF. The study population for this clinical trial will be comprised of adult patients who have been diagnosed with stage 2 resistant hypertension. In addition, these patients must satisfy the inclusion and exclusion criteria. The trial will prospectively enroll up to 20 subjects. Patients presenting with stage 2 resistant hypertension must be on a minimum of three (3) anti-hypertensive medications. Clinical site personnel will review the patient's medical history for eligibility. Potential candidates will be fully informed by a member of the research team as to the purpose of the study and the nature of the implantation procedure. The implantation procedure will be described and its potential risks and benefits will be explained in detail. Patients who voluntarily agree to participate in the trial will be asked to sign and date the written Informed Consent Form (ICF). If approved by the reviewing IRB/EC, subjects may indicate verbal, witnessed consent with the signature of a patient representative not associated with the study team if cognition is intact but the subject is unable to sign (e.g., the subject has inhibited hand function or visual disturbance).

The approved ICF must be signed for study enrollment prior to performing study related assessments. A copy of the signed and dated ICF should be provided to the subject. Subjects must be informed that they may withdraw from the study at any time, and for any reason, and will continue to receive therapy as indicated by their physician. Internet-based Case Report Forms must be completed for each subject who consents to study participation.

8.5 BASELINE ASSESSMENT: VISIT 1 (DAY 0-14) – ASSESSED DAY 14

The following information will be assessed and the documentation will be maintained as source records at the study site:

- Medical history;
- Office cuff blood pressure (Note: Office cuff BP recordings must be performed as detailed in Appendix IV);
- Check for orthostatic blood pressure and orthostatic pulse assessments;
- Daily patient diary assessments of blood pressure and medication compliance;

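### Section 7.0 sets no boundary for subjects excluded at the procedure-day angiogram, so an SAE in a subject accessed but not implanted can be left out of the primary safety result

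*Combined protocol and SAP*

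**What the plan says.** Three rules bear on a subject who consents but receives no implant.

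- Section 7.0 defines a screen failure as a subject who signed consent but did not meet every eligibility criterion. It then states: "No CRFs are required to be completed for screen failure patients and these patients will not be followed per the Investigational Plan requirements".
- The closing paragraph of Section 7.0 states: "If the Investigator is unable to place a MobiusHD implant in a subject, the subject will be followed to the 30-Day visit". Follow-up is longer if an adverse event is ongoing, and the reason for failure goes on the Procedure CRF.
- Section 8.4 states: "Internet-based Case Report Forms must be completed for each subject who consents to study participation".

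On enrolment, Section 7.0 says: "All subjects who meet the eligibility criteria and give written informed consent are considered enrolled in the study".

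Some criteria are settled only on the procedure day. Section 6.2 lists four angiographic exclusions, the first being: "Evidence of plaque, ulceration or any stenosis by angiographic evaluation in orthogonal views of the carotid artery". Section 6.1 allows the renal artery criterion to be met by earlier imaging, by a duplex before enrolment, "or by performing nonselective renal angiography at the time of device implantation".

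The primary outcome in the Synopsis is the incidence of SAEs and UADEs "reported for the study population from implantation through six (6) months of follow-up". Section 13.0 plans no formal test, gives numbers and percentages of patients with adverse events, and names no analysis set or denominator.

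**The concern.** The primary outcome is safety, and the device cannot be placed without this angiogram. A stroke, vessel dissection or access-site bleed during the angiogram is a risk of the treatment strategy even when the device is never released. If the screen-failure rule is applied to such a subject, the protocol requires no CRF and no later visit, and the subject may not count as enrolled.

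Two sites could also treat the same subject differently. One would close the record on the table; the other would follow to Day 30. In a descriptive study of up to 20 subjects the SAE tabulation is the primary result, so one event decides whether the report shows no SAEs or some.

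**Working it through.** The plan states no figure that could be reproduced: there is no alpha, power or effect size, and no formula behind the 20 subjects. The check is a comparison of the text, followed by an illustration.

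**Step 1: when eligibility is decided.** Under Section 8.8, subjects who pass the earlier checks go to the angiogram so that the remaining criteria can be assessed, and may be treated in that session if all are met. Section 8.9 puts arch and selective carotid angiography before the decision to proceed. Final eligibility is therefore settled after arterial access.

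**Step 2: which rule applies.**

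| Rule | Covers | CRF | Follow-up |
|---|---|---|---|
| 7.0, screen failures | consented, failed any criterion | none | none |
| 7.0, closing paragraph | investigator unable to place the implant | Procedure CRF | Day 30, longer if an AE is ongoing |
| 8.4 | everyone who consents | iCRFs | not addressed |

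Section 6.2 opens: "Candidates will be ineligible for enrollment in the study if any of the following conditions are identified at the screening or baseline visits". Section 8.7 labels the procedure day as baseline Visit 3. An angiographic exclusion therefore fits the first row. Angiographic exclusion 3, carotid bifurcation anatomy unsuitable for deployment, fits the second row equally well. Every such subject fits the third. No visible text says which row governs.

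**Step 3: the primary outcome.** It depends on two terms.

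- *Study population.* Section 6.0 describes the clinical population and ties it to eligibility, but it is not an analysis set. Section 7.0 counts as enrolled only those who meet the criteria. A subject excluded on the table may thus be outside it.
- *Implantation.* It is not among the protocol's definitions. Section 8.9 speaks of the angiogram and the implantation as two procedures, Section 8.17 joins them with a slash, and Section 6.1 places renal angiography at the time of implantation although it comes before device release.

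If the subject is outside the study population, the SAE is omitted however implantation is defined. If the subject is inside it, the start of the window decides.

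**Step 4: illustration with assumed counts.** Assume 2 to 5 subjects are accessed but not implanted, with one SAE among them and none among the implanted, all counted through Day 30. Intervals are exact (Clopper-Pearson) 95% intervals. With no events the upper limit is 1 − 0.025^(1/n); for n = 20 this is 16.8%. With x ≥ 1 events the limits are the 2.5% quantile of Beta(x, n − x + 1) and the 97.5% quantile of Beta(x + 1, n − x).

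| Assumption | Left out | Counted |
|---|---|---|
| Replaced, 2 excluded | 0/20 = 0% (0 to 16.8%) | 1/22 = 4.5% (0.1 to 22.8%) |
| Replaced, 5 excluded | 0/20 = 0% (0 to 16.8%) | 1/25 = 4.0% (0.1 to 20.4%) |
| Not replaced, 2 excluded | 0/18 = 0% (0 to 18.5%) | 1/20 = 5.0% (0.1 to 24.9%) |
| Not replaced, 5 excluded | 0/15 = 0% (0 to 21.8%) | 1/20 = 5.0% (0.1 to 24.9%) |

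The percentage can also move the other way. With 2/20 = 10.0% among the implanted, adding 5 event-free excluded subjects gives 2/25 = 8.0%.

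The table supposes that an SAE occurs. If each such subject has an assumed risk p of 1% to 5%, the chance of at least one SAE among k subjects is 1 − (1 − p)^k. This runs from 1 − 0.99² = 2% to 1 − 0.95⁵ = 23%.

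**Step 5: unequal windows.** A subject under the closing paragraph of Section 7.0 with no ongoing event leaves at Day 30, which is 180 − 30 = 150 days before the 180-day visit. A pooled six-month percentage would mix two lengths of observation.

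**The case against.** The strongest reply is that Section 7.0 reconciles itself. Its closing paragraph follows the screen-failure rule and is more specific, so screening failures would fall under the first and procedure-day failures under the second. That is a sensible reading, and Figures 7 and 8, which chart screening and enrolment and are not shown, may depict it. The point is therefore a missing boundary in the visible text; a reader might infer rules that cannot both stand, and the documents do not support that.

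A reader might also infer that such an SAE would vanish. They do not support that either. Section 8.10 monitors for peri-procedural events, Section 11.1 covers any intervention the protocol imposes, Section 11.4 sends SAEs to the sponsor, and Sections 11.5 and 16.1 send them to the DSMB. Section 8.9 expects assessment data in the database before implantation, and Section 13.0 promises a narrative alongside the CRF fields. What remains is that none of these puts the event in the primary result or gives it a denominator. Section 11.0 also starts reporting at initial treatment and Section 11.2 refers to study treatment, both undefined.

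Third, excluded subjects may be few, because CTA or MRA and carotid duplex at Visit 2 already screen for obstructive disease and vessel diameter. That limits the expected size and stands.

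Finally, this is a pilot without formal testing or a numerical safety threshold. No inference is invalidated, but a descriptive primary count still needs a defined population and start.

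**Conclusion.** The concern holds as a gap in definition that is worth correcting. The visible text overlaps on subjects accessed and then excluded, and one literal reading leaves a procedure-day SAE out of the primary safety result. The main causes are the open-ended screen-failure rule and a study population not fixed for analysis; a reader might blame the undefined start of implantation alone, but defining it would not bring in a subject who is not in the population.

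The size is not computable: the documents give no angiographic exclusion rate and do not say whether excluded subjects are replaced. The direction for the count is certain, since omission can only lower it. The percentage can go either way once the groups are pooled. All counts and risks in the illustration are assumptions, and it should not be read as evidence that the reported rate would be biased by those amounts.

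**What to change.** 1. Reconcile the two rules in Section 7.0 with Section 8.4, so that the waiver of CRFs and follow-up covers only subjects who fail before arterial access. Later non-implanted subjects would come under the existing closing paragraph of Section 7.0. Check that Figures 7 and 8 agree.
2. State in the Synopsis that the primary safety window starts at arterial access for the study procedure, and say in Section 13.0 which subjects form the safety population.
3. Report SAEs and UADEs separately, each with its own denominator, for implanted subjects through six months and for accessed-but-not-implanted subjects through Day 30. Give any combined figure only through Day 30.

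The cost is protocol wording, CRFs and a Day 30 visit for a few extra subjects, and an SAE count that may look less favourable.

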8.0 STUDY METHODS

The study assessments, beginning with the baseline assessments used for screening potential study participants, are described below by visit.

8.1 MEDICAL THERAPY REGIMEN – ALL SUBJECTS

All participants in the study will be on a minimum of three (3) anti-hypertensive drugs such as, but not limited to, the following:

Diuretics			
Class	Generic name	Brand name	Side effects
Thiazide diuretics	chlorothiazide	Diuril	Weakness, confusion, potassium depletion, gout, fatigue, thirst, frequent urination, lightheadedness, muscle cramps, diarrhea or constipation, increased sensitivity to sunlight, allergic reaction in people allergic to sulfa drugs, impotence.
	chlorthalidone	Hygroton	
	hydrochlorothiazide	Esidrix, HydroDiuril, Microzide	
	indapamide	Lozol	
	metolazone	Mykrox, Zaroxolyn	
Loop diuretics	bumetanide	Bumex	Weakness, confusion, potassium depletion, gout, fatigue, thirst, diarrhea or constipation, increased sensitivity to sunlight, allergic reaction in people allergic to sulfa drugs, impotence.
	ethacrynic acid	Edecrin	
	furosemide	Lasix	
	toremide	Demadex	
Potassium-sparing diuretics/ aldosterone-receptor blockers*	amiloride	Midamor	Excessive potassium levels, especially in patients with kidney disease; breast enlargement and erectile dysfunction in men; menstrual irregularities in women.
	spironolactone	Aldactone	
	triamterene	Dyrenium	
	eplerenone	Inspra	Headache, dizziness, diarrhea, fatigue, upset stomach, and breast enlargement or tenderness.

*Note: Potassium-sparing diuretics also directly or indirectly block aldosterone, a hormone that raises blood pressure by causing the kidneys to conserve sodium and water. As a result, these four medications are sometimes also known as aldosterone-receptor blockers. Amiloride (Midamor), spironolactone (Aldactone), and triamterene (Dyrenium) also affect other hormones and thus carry some unwanted side effects, such as breast enlargement and impotence in men and menstrual irregularities in women. Eplerenone (Inspra) is the only one of these medications that affects solely aldosterone and not other hormones.
			

Anti-adrenergic drugs			
Class	Generic name	Brand name	Side effects
Beta blockers (cardioselective)	atenolol	Tenormin	Wheezing, dizziness, depression, impotence, fatigue, insomnia, decreased HDL cholesterol levels, lower exercise tolerance. Can worsen peripheral vascular disease and heart failure. Abrupt withdrawal may trigger angina or a heart attack in patients with heart disease.
	metoprolol	Lopressor	
	metoprolol extended release	Toprol-XL	
	nebivolol	Bystolic	
Beta blockers (nonselective)	nadolol	Corgard	
	pindolol	Visken	
	propranolol	Inderal, Inderal LA	
	sotalol	Betapace	
	timolol	Blocadren	
Alpha-1 blockers	doxazosin	Cardura	A drop in blood pressure upon standing up, fainting, weakness, heart palpitations, headache, nasal congestion, dry mouth.
	prazosin	Minipress	
	terazosin	Hytrin	
Alpha and beta blockers	carvedilol	Coreg	Wheezing, depression, insomnia, diarrhea, lightheadedness, dizziness, unusual tiredness or weakness, drying of the eyes, erectile dysfunction, headache, dry mouth, nasal congestion, decreased HDL cholesterol levels, lower exercise tolerance, a drop in blood pressure upon standing up, fainting, heart palpitations. Can worsen peripheral vascular disease and heart failure. Abrupt withdrawal may trigger angina or a heart attack in patients with heart disease.
	labetalol	Normodyne, Trandate	
Peripheral nerve-acting agents	guanethidine	Ismelin	A drop in blood pressure upon standing up, depression, nasal stuffiness, nightmares. Guanethidine may slow heart rate and reserpine may cause indigestion.
	reserpine	Serpalan	

Direct-acting vasodilators		
Generic name	Brand name	Side effects
hydralazine	Apresoline	Headaches, palpitations, weakness, flushing, nausea. Minoxidil may cause hair growth, fluid retention, and increased blood sugar.
minoxidil	Loniten	
Calcium-channel blockers		
Generic name	Brand name	Side effects
amlodipine	Norvasc	Headache, dizziness, edema, and heartburn. Nifedipine can cause palpitations. Diltiazem and verapamil can cause constipation and a slowed heartbeat.
diltiazem	Cardizem, Dilacor, others	
felodipine	Plendil	
isradipine	DynaCirc	
nicardipine	Cardene, Cardene SR	
nifedipine	Adalat CC, Procardia XL	
verapamil	Calan, Isoptin, others	
ACE inhibitors		
Generic name	Brand name	Side effects
benazepril	Lotensin	Cough, rash, fluid retention, high potassium levels, and loss of taste. May cause low blood pressure and fainting. Can worsen kidney impairment if narrowed arteries feed both kidneys. May cause fetal abnormalities.
captopril	Capoten	
enalapril	Vasotec	
fosinopril	Monopril	
lisinopril	Prinivil, Zestril	
quinapril	Accupril	
ramipril	Altace	

Angiotensin-receptor blockers (ARB)		
Generic name	Brand name	Side effects
candesartan	Atacand	Muscle cramps, dizziness.
eprosartan	Teveten	
irbesartan	Avapro	
losartan	Cozaar	
olmesartan	Benicar	
telmisartan	Micardis	
valsartan	Diovan	
Combination antihypertensive drugs		
Class	Generic name	Brand name
Potassium-sparing and thiazide diuretics	amiloride + HCTZ*	Moduretic
	spironolactone + HCTZ	Aldactazide, Spironazide, Spirozide
	triamterene + HCTZ	Dyazide, Maxzide
Alpha blocker and diuretic	prazosin + polythiazide	Minizide
Beta blocker and diuretic	atenolol + chlorthalidone	Tenoretic
	bisoprolol + HCTZ	Ziac
	metoprolol + HCTZ	Lopressor HCT
	nadolol + bendroflumethiazide	Corzide
	propranolol + HCTZ	Inderide, Inderide LA
	timolol + HCTZ	Timolide
ACE inhibitor and diuretic	benazepril +HCTZ	Lotensin HCT
	captopril + HCTZ	Capozide
	enalapril + HCTZ	Vaseretic
	fosinopril + HCTZ	Monopril HCT

Class	Generic name	Brand name
ACE inhibitor and diuretic (continued)	lisinopril + HCTZ	Prinzide, Zestoretic
	moexipril + HCTZ	Uniretic
	quinapril + HCTZ	Accuretic
ARB and diuretic	candesartan + HCTZ	Atacand HCT
	eprosartan + HCTZ	Teveten HCT
	irbesartan + HCTZ	Avalide
	losartan + HCTZ	Hyzaar
	telmisartan + HCTZ	Micardis HCT
	valsartan + HCTZ	Diovan HCT
Calcium-channel blocker and ACE inhibitor	amlodipine + benazepril	Lotrel
	diltiazem + enalapril	Teczem
	felodipine + enalapril	Lexxel
	verapamil + trandolapril	Tarka
Other combinations	methyldopa + HCTZ	Aldoril
	reserpine + chlorothiazide	Diupres
	reserpine + HCTZ	Hydropres
	aliskiren + HCTZ	Tekturna HCT
Calcium-channel blocker and ARB	amlodipine + valsartan	Exforge
	amlodipine + olmesartan	Azor
*HCTZ=hydrochlorothiazide		

Medications for treating hypertension
http://www.health.harvard.edu/newsletters/Harvard_Womens_Health_Watch/2009/August/Medications-for-treating-hypertension
 (downloaded on 7/3/2012)

All subjects that are implanted with the MobiusHD will be required to be on dual antiplatelet therapy (ie. aspirin 81-325 mg daily and clopidogrel 75 mg daily; substitutes can be used but should be equivalent) for three (3) days prior to the implant procedure as well as three (3) months post-procedure. Aspirin will continue for the duration of study.

Management of subject's individual risk factors as appropriate, e.g., statins, smoking cessation, nutritionist, diabetes management, etc., will remain as standard of care and any changes to this regimen will be documented by the study team.

Subjects should be advised of the importance of not stopping their medical therapy regimen before first consulting with the study center. In the absence of changes initiated by the study physician in response to severe symptomatic drops in blood pressure, subjects should not reduce or stop their anti-hypertensive medication dosage until the 6-month time point, at which time the Principle Investigator may decide to reduce medication use.

